9.2 Trial Specific Safety Assessments

Overall assessment of tolerability by the patient and by the investigator on days 7 (Visit 4) and Day 15 (Visit 6).

➤ **Patient's assessment of the overall tolerability**

The patient will assess the overall tolerability during the visit on days 7 (Visit 4) and 15 (Visit 6).

The patient will rate the tolerability using a five-point rating scale: ① = very poor, ② = poor, ③ = medium, ④ = good, ⑤ = very good. The investigator will document the patient assessment of overall tolerability in the CRF.

➤ **Investigator's assessment of the overall tolerability**

The investigator will assess the overall tolerability on days 7 (Visit 4) and 15 (Visit 6).

The investigator will rate the tolerability using a five-point rating scale: ① = very poor, ② = poor, ③ = medium, ④ = good, ⑤ = very good.

Adverse Events (AEs) and Serious Adverse Events (SAEs): AEs will be recorded by the investigator at each visit until the end of the double-blind phase inclusive the follow-up phone call (within 7 days after Visit 6 or earlier in case of premature termination). AEs will be assessed for seriousness, severity and drug-event relationship (details are provided in section 9.3).

Vital signs: Blood pressure, pulse rate, and body temperature will be recorded at each visit: at screening (Visit 1), immediately before randomization (Visit 2; this will constitute the baseline value), and on days 4 (Visit 3), 7 (Visit 4), 10 (Visit 5), and 15 (Visit 6).

ENT examination of nose (septum, mucosa, secretion, obstruction, polyps); **ears** (effusion and erythema), **mouth/ throat** (anterior and posterior discharge, dental abnormalities and halitosis) will be recorded at screening (Visit 1), on Day 7 (Visit 4) and on Day 15 (Visit 6).

Safety laboratory examination of blood at screening (Visit 1) and end of treatment (Visit 6) for the following:

Hematology: hemoglobin, hematocrit, leukocytes with differential count, erythrocytes, erythrocyte sedimentation rate, MCV, MCH, MCHC, and platelet count

Blood chemistry:

Electrolytes sodium, potassium, serum calcium, serum albumin, chloride

Substrates creatinine, total protein, total bilirubin, blood glucose, urea, uric acid

Enzymes ALT, AST, γ -GT, ALP

Pregnancy test: In all women a serum pregnancy test for measurement of human chorionic gonadotropin (hCG) will be performed at screening (Visit 1) and at Visit 6.

9.3 Adverse Events

9.3.1 Definitions

An **Adverse Event / Experience (AE)** is any untoward medical occurrence in a patient or clinical investigation subject administered a pharmaceutical product and which does not necessarily have to have a causal relationship with this treatment.

An adverse event (AE) can therefore be any unfavorable and unintended sign (including an abnormal laboratory finding, for example), symptom, or disease temporally associated with the use of a medicinal product, whether or not considered related to the medicinal product.

A **Serious Adverse Event (SAE)** is any untoward medical occurrence that at any dose:

- results in death
- is life-threatening
- requires inpatient hospitalization or prolongation of existing inpatient hospitalization
- results in persistent or significant disability/ incapacity
- is a congenital anomaly/ birth defect
- is medically significant: Medical and scientific judgment should be exercised in deciding whether expedited reporting is appropriate in other situations, such as important medical events that may not be immediately life-threatening or result in death or hospitalization but may jeopardize the subject (patient) or may require intervention to prevent one of the other outcomes listed above. These should also usually be considered serious.

These characteristics/consequences have to be considered at the time of the event. For example, regarding a life-threatening event, this refers to an event in which the subject was at risk of death at the time of the event; it does not refer to an event which hypothetically might have caused death if it were more severe.

A **(Serious) Adverse Drug Reaction ((S)ADR)** is any (S)AE for which the investigator or sponsor assess a reasonable possibility for a causal relationship to a medicinal product, see [9.3.3](#) below.

A **(Serious) Unexpected Adverse Reactions** is defined as a (serious) adverse drug reaction, the nature or severity of which is not consistent with the Reference Safety Information (SmPC).

The term 'severity' is used here to describe the intensity of a specific event. This has to be distinguished from the term 'serious'. Reports which add significant information on the specificity, increase of occurrence, or severity of a known, already documented serious adverse reaction constitute unexpected events.

Information about common side effects already known about the Investigational Medicinal Product (IMP) can be found in the Reference Safety Information (SmPC) or will be communicated in the form of Investigator Notifications. This information will be included in the subject information and should be discussed with the subject.

For further details, please refer to the Quick Reference Guide for completing the Serious Adverse Event Form.

9.3.2 Severity of Adverse Events

The term 'severity' is used here to describe the intensity of a specific event. This has to be distinguished from the term 'serious'. In the course of the trial, the investigator will determine whether any AE have occurred and will grade their severity as follows:

- Mild Usually transient in nature and generally not interfering with normal activities
- Moderate Sufficiently discomforting to interfere with normal activities
- Severe Prevents normal activities

9.3.3 Relationship to the IMP

The investigator should evaluate all AEs considering all accessible data, at any time new information becomes available. The definition of IMP includes the test product under evaluation or the placebo that is given during any phase of the trial.

The investigator should assess whether or not, in his/her expert opinion, the AE is suspected to the drug. Suspected means that a causal relationship between the drug and an adverse event is at least a reasonable possibility, i.e. the relationship cannot be ruled out.

Causality assessments are critical and must be provided for each unique AE in relation to each IMP, non-investigational medicinal product (NIMP) or other concomitant medication, if applicable. Missing causality assessments will be handled as suspected to IMP by the sponsor.

AEs with a suspected relationship to NIMP or other concomitant medication (for both Sandoz and non-Sandoz products), even if non-serious, need to be reported by the investigator to the respective Country Patient Safety Head (see section [9.3.5](#) for contact details).

9.3.4 Adverse Events Documentation

Any AE (non-serious and serious) occurring after the subject has provided study-specific informed consent and until the last study visit of the subject, has to be recorded on the AE pages of the Case Report Form (CRF).

The occurrence of AEs should be sought by non-directive questioning of the subject at each visit during the study. AEs also may be identified when they are volunteered by the subject during or between visits or during physical examination, laboratory test or other assessments. All AEs should be given appropriate medical care. Treatment may include one or more of the following: no action taken (i.e. further observation only); IMP dosage adjusted/temporarily interrupted; IMP permanently discontinued due to this AE; concomitant medication given; non-drug therapy given, patient hospitalized / patient's hospitalization prolonged. The treatment of the AE should be documented in the CRF. In addition, the action taken with the IMP should be documented, and should be assigned to one of the following categories: not changed, withdrawn, reduced, increased, interrupted, unknown and not applicable.

Concomitant medication, other treatments or changes in the administration of the IMP should be specified and documented.

Medical conditions/diseases present before starting IMP are only considered AEs if they worsen after enrolment. Abnormal laboratory values or test results constitute AEs only if they induce clinical signs or symptoms, are considered clinically relevant, or require therapy.

Once an AE is identified, the investigator should follow-up as specified below. Each time, the outcome should be documented and assigned to one of the following categories: not recovered/unchanged, condition deteriorating, recovered/resolved, improving/recovering, recovered/resolved with sequelae, fatal or unknown. The assessment of an AE should be made at each planned visit (or more frequently, if necessary). The investigator should document in the CRF any changes in seriousness, severity, the suspected relationship with the IMP, the interventions required to treat it, and the outcome.

Adverse events occurring between informed consent and the last visit

The investigator should follow up on all AEs which occurred from signature of study-specific informed consent until the last visit of the subject, at which point the outcome assessment is documented in the CRF.

Ongoing serious adverse events at the time of last visit

For any SAEs still ongoing at the time of last visit, the investigator should continue to follow-up until the SAE has resolved or has stabilized / is judged permanent for SAEs considered to be related to IMP (SADRs), and for up to 30 days after the last visit of subject for non-related SAEs. The investigator should send SAE follow-up reports to recipients as per the 'SAE Reporting' section 9.3.5 below.

Serious adverse events occurring after the last visit

Any SAEs experienced after the last visit should only be reported to sponsor if the investigator suspects a causal relationship to study treatment. The investigator must report the SADR to recipients as per the 'SAE Reporting' section 9.3.5 below.

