6.4.2 Pharmacokinetics

*Absorption*¹⁵

Following oral administration, acetylcysteine is rapidly and almost completely absorbed and metabolized in the liver to cysteine, the pharmacologically active metabolite, as well as to diacetylcysteine, cystine and further mixed disulphides.

*Distribution*¹⁵

Due to the high first-pass effect, the bioavailability of orally administered acetylcysteine is very low (approx. 10%). In humans, maximum plasma concentrations are achieved after 1-3 hours with the maximum plasma concentration of the metabolite cysteine in the range of approx. 2 µmol/l. The protein binding of acetylcysteine was determined to be about 50%.

*Biotransformation*¹⁵

Acetylcysteine and its metabolites occur in three different forms in the organism: partially in free form, partially bound to proteins via labile disulphide bonds and partially as incorporated amino acid. Acetylcysteine is excreted almost exclusively in the form of inactive metabolites (inorganic sulphates, diacetylcysteine) via the kidneys. The plasma half-life of acetylcysteine is approximately 1 hour and is mainly determined by the rapid hepatic biotransformation. Impaired hepatic function therefore leads to prolonged plasma half-lives of up to 8 hours.

*Elimination*¹⁵

Pharmacokinetic studies with intravenous administration of acetylcysteine revealed a distribution volume of 0.47 l/kg (in total) or 0.59 l/kg (reduced); the plasma clearance was determined to be 0.11 l/h/kg (in total) and 0.84 l/h/kg (reduced), respectively. The elimination half-life after intravenous administration is 30-40 minutes while excretion follows three-phase kinetics (alpha, beta, and terminal gamma phase).

Acetylcysteine crosses the placenta and is detected in cord blood. No information is available regarding excretion into breast milk.

No knowledge is available concerning the behaviour of acetylcysteine at the blood-brain barrier in humans.

7 Trial Objectives

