FOLLOW-UP PHONE CALL (within 7 days after Visit 6 or earlier in case of premature termination)

- date of phone call
- check of adverse events after Visit 6.

During the phone call the investigator will check if any AE occurred after Visit 6 and if medically required the patient can be invited for additional (not trial related) visits. The results of these additional examinations and treatments will remain in the individual medical health records/ files of the clinical center(s) only. The date of the last follow up call of the last patient in the trial will be defined as the end of the trial.

In case that the investigator cannot reach the patient for the final follow-up call, he/she will document this in the CRF.

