10.4 Statistical Tests

██████████ will write the **Statistical Analysis Plan (SAP)** for the present trial.

Efficacy:

Efficacy of the test product will be shown by testing superiority of the three different doses in a hierarchical test procedure from the highest to the lowest dose compared to placebo.

Hierarchical ordered hypotheses will be tested at the type I error rate of $\alpha=0.05$ (two-sided) until the first non-rejection. No error rate adjustment is required.

The set of hypotheses is as follows:

$$H_{01}: \mu_{2400} = \mu_{PL}$$

$$H_{11}: \mu_{2400} \neq \mu_{PL}$$

$$H_{02}: \mu_{1200} = \mu_{PL}$$

$$H_{12}: \mu_{1200} \neq \mu_{PL}$$

$$H_{03}: \mu_{600} = \mu_{PL}$$

$$H_{13}: \mu_{600} \neq \mu_{PL}$$

Where μ notes “mean change from baseline in the daily MSS over the entire treatment period” for the respective strength.

Superiority of the Test treatment over placebo (PL) is confirmed if the p-value is < 0.05 and a positive treatment effect is shown.

For the primary efficacy an endpoint, analysis of covariance (ANCOVA) will be carried out using treatment and center as factors and baseline MSS as a covariate.

The trial will be powered to demonstrate superiority of the test product over placebo in the primary efficacy endpoint.

The confirmatory analysis of the primary endpoint will be performed in the FAS.

In addition, the analyses used for the primary efficacy endpoint will be performed in the PPS.

This analysis is intended to provide supportive evidence and will be considered descriptive.

Safety:

The Safety Set will be used for the analysis of the safety data. All safety data obtained in this trial will be tabulated descriptively with descriptive group statistics (mean, standard deviation, minimum, maximum, number of valid cases) where appropriate.

AEs will be summarized by primary system organ class (SOC) and preferred term (PT). Severity and drug-event relationship of treatment emergent AEs are summarized separately. All adverse events will be listed.

Vitals signs, including changes from baseline will be summarized. A frequency table will be presented for abnormal values of laboratory parameters.

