7.3.3.1 Adverse Events

An **adverse event or adverse experience (AE)** is any untoward medical occurrence in a patient or clinical investigation patient administered a pharmaceutical product and which does not necessarily have to have a causal relationship with this treatment.

An adverse event (AE) can therefore be any unfavorable and unintended sign (including an abnormal laboratory finding), symptom, or disease temporally associated with the use of a medical product, whether or not considered related to the medical product.

Existing concomitant diseases are not considered AEs, except if they have worsened/adversely progressed during the study.

The Medical Dictionary for Regulatory Activities (MedDRA, Version 22.1 or higher) is used for coding adverse events.

All AEs with start date/time prior to first intake of IMP are pre-treatment AEs and will be assigned to screening.

Any adverse events with missing start date/time or the end date/time are treated as follows:

- If the date is known but the time is unknown, the time will be imputed with a time 0:00 h for the start and with 23:59 for the end. In the listings the unknown time will be displayed as NK. If the start date is a treatment date, then the AE will be assigned to the treatment of that date.
- If the start date is incomplete:
 - Missing day: will be imputed with the 1st of the month unless month is the same month of first dose of study drug; then it will be imputed with first dose date
 - Missing day and month: will be imputed with 1st January unless year is the same as first dose date; then it will be imputed with first dose date
 - Completely missing: impute first dose date unless the end date suggests it could have started prior to this in which case the 1st January of the same year will be imputed as the start date
- If the end date is incomplete:
 - Missing day: will be imputed with the last day of the month unless month is same as month of first dose of study drug; then it will be imputed with the last dose date
 - Missing day and month: will be imputed with 31st December unless year is the same as first dose date; then it will be imputed with last dose date
 - Completely missing (and not ONGOING): if the AE started prior to 1st dose date then it will be imputed the 1st dose date. If the AE started after 1st dose date then it will be imputed with the last dose date

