The pre-treatment adverse events which occurred before intake of the first dose of IMP (between screening visit (Visit 1) on Day -1 and Visit 2 on Day 1) will be presented in listings.

The adverse events will be analyzed by means of frequency tables. For an overview a frequency table with numbers of patients affected will be presented by treatment for the categories (Summary of adverse events): total, adverse events leading to discontinuation, serious adverse events, and (serious) adverse events with outcome death.

Further frequency tables will be classified by system organ class (SOC), preferred term (PT) derived from MedDRA and by treatment. The numbers of adverse events as well as the numbers of patients affected will be presented.

Moreover, tables for incidences of adverse events and patients with respect to the following parameters will be created:

- Severity (mild, moderate, severe),
- Relationship between study medication and adverse event (suspected, not suspected),
- Outcome (not recovered / not resolved / unchanged; recovered / resolved, improving/ recovering/ resolving; recovered with sequelae; fatal; condition deteriorating; unknown).

All adverse events will be listed, these listings will be split into three parts containing the following columns:

Part I: Rnd. No. , Report No., Observed AE (in verbatim), Seriousness, Action taken with IMP; Severity, Outcome, Relationship to IMP, Relationship to NIMP

The report number is an identifier for the single adverse events within one patient (chronologically).

This part I will be displayed in two versions:

- first version is sorted by treatment group (where pre-treatment adverse events will be pooled as additional group), random number and report number,
- in the second version the adverse events are sorted by random number and report number.

The second and third part will only be displayed sorted by random number and report number with the following information:

Part II: Rnd. No., Report No., MedDRA Coding: Preferred Term (with Code), Date/Time of onset, Date/Time of end, Last date/time of dose before onset, Last treatment.

Part III: Rnd. No, Report No, Event treatment, Specification of event treatment.

These adverse events will be listed for the safety set. If patients experience adverse events who were not randomized, or had no intake of IMP then further listing for these events will be displayed.

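### The SAP classes adverse events by start date alone, so an event that begins between consent and first dose and then worsens on drug is, on a natural reading, left out of the by-arm AE tables

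*Protocol*

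**What the plan says.** **Assignment rule.** SAP 7.3.3.1 separates events by onset only: "All AEs with start date/time prior to first intake of IMP are pre-treatment AEs and will be assigned to screening". No later sentence moves such an event to a treatment arm if it gets worse.

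**Where those events are reported.** The same section says of the events with onset before the first dose ("between screening visit (Visit 1) on Day -1 and Visit 2 on Day 1) will be presented in listings") that listings are their place. In the version of listing Part I sorted by treatment group they sit apart from the arms: "where pre-treatment adverse events will be pooled as additional group". SAP 8.1 names a listing of pre-treatment AEs and no table for them. The frequency tables (SOC/PT, severity, relationship, outcome) are by treatment.

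**How worsening is recorded.** Protocol 9.3.4, on an AE already identified: "The investigator should document in the CRF any changes in seriousness, severity, the suspected relationship with the IMP".

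**What the protocol promises.** Synopsis and section 10.4: "Severity and drug-event relationship of treatment emergent AEs are summarized separately". Neither document defines treatment-emergent.

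**When collection ends.** Protocol 9.3.4 stops CRF recording of AEs at the patient's last study visit. The synopsis, 8.2 and 9.2 run it to the follow-up call, up to 7 days after Visit 6. The call in section 9 includes a "check of adverse events after Visit 6".

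**The concern.** Collection starts at consent, so some events will already be open at the first dose. Whether such an event then worsens is a question about the drug, and the randomised comparison is the place to answer it. A rule that looks only at the start date settles the event's place before the drug could have affected it.

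Safety and tolerability are the trial's secondary objective, and the safety endpoints include incidence and severity of AEs. If on-drug worsening of an already open event is filed under screening, the by-arm severity and causality tables omit events that the protocol's promised treatment-emergent summaries would be expected to contain. A reader of those tables could not tell that they were missing.

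**Working it through.** No sample size, power or alpha figure depends on this rule, so there is no stated figure to reproduce. The check is a reading of the rules in sequence, with a bound on the size of the window.

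1. **Follow one event.** Suppose an AE starts, mild, on the evening of Day -1 and becomes severe or serious on Day 5. Its start precedes first intake, so SAP 7.3.3.1 assigns it to screening. The change on Day 5 does not alter the start date.

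2. **Does worsening open a new record with a new onset?** Neither document says so. Protocol 9.3.4 speaks of documenting changes in an event already identified, which suggests an update. Protocol 9.3.5 points the same way for safety reports: progression of an SAE goes in as follow-up to the original episode. That sentence covers only events that were already serious. So the update reading is the natural one, but it is an inference.

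3. **Result for the tables.** As an updated record, the event appears in the pre-treatment listing and, if serious, in the SAE listing. It is not counted under an arm in the SOC/PT, severity or relationship tables. The same event with onset one hour after the first dose would be counted there. The SAP does not state in words that pre-treatment AEs are left out of the by-arm tables. It follows from their assignment to screening and their pooling as a separate group.

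4. **Size of the window.** Protocol 8.5.2 puts screening within one day before randomisation, so the pre-dose window is about 1 day if consent is given at Visit 1. With T the days from first dose to the end of collection, its share of observation time is 1/(1 + T). I assume first dose at 08:00 on Day 1 and collection ending at 12:00:

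| End of collection | T (days) | Share |
|---|---|---|
| Visit 6 on Day 15 | 14.17 | 1/15.17 = 6.6% |
| Visit 6 on Day 18 | 17.17 | 1/18.17 = 5.5% |
| Call on Day 22 | 21.17 | 1/22.17 = 4.5% |
| Call on Day 25 | 24.17 | 1/25.17 = 4.0% |

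At a constant onset rate, about 4 to 7% of AEs would therefore start before the first dose. The misplaced events are the part of these that later worsen or become serious. The documents give no figure for that part, so only the bound can be stated.

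5. **End of collection.** For a non-serious event starting between Visit 6 and the call, Protocol 9.3.4 asks for no CRF record, while 9.2 has it recorded. Both cannot apply.

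**The case against.** **Exclusion from the tables is inferred.** True. Protocol 9.3.13 even commits to tabulating all adverse experiences by severity, treatment and causality. But that supports the change: the SAP rule, as written, does not deliver it.

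**The events are not lost.** This stands. They are listed, SAEs are listed whatever their onset, and SAP 7.3.4.1 tabulates drop-out reasons, adverse event among them, by arm with no start-date condition. A reader might infer that worsening on drug disappears from the report; it does not.

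**The gap is narrow.** This stands too. AE questioning and an eligibility check take place at Visit 2 before dosing. The SAP's imputation rules also send an event of unknown time on a treatment date to treatment, and a missing start day in the month of first dose to the first-dose date.

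**Aggravated pre-existing disease.** One might infer that it keeps its old onset date and so drops out as well. The documents do not support that. Protocol 8.4.2.1 and 9.3.4 and SAP 7.3.3.1 treat the aggravation itself as the AE, and the form on which its date is entered is not among the documents. What remains is that the onset date for such an event is not stated.

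**Follow-up events.** One might also infer that counting events up to the call is an error, because "The plasma half-life of acetylcysteine is approximately 1 hour", and that it dilutes the comparison. It is a legitimate choice applied alike to all four arms. Half-life does not bound attribution: the same section gives up to 8 hours with impaired hepatic function, and the adverse reactions in 8.3.1 include hypersensitivity. The SAP plans AE counts and numbers of patients affected, with no between-arm test. For illustration only, assume a background AE rate b per 14 days and a true excess of 5.0 points on drug. After d off-drug days the absolute difference is 5.0 × (1 − b)^(d/14). With b = 10% that is 4.7 points (d = 8) or 4.6 (d = 11); with b = 20%, 4.4 or 4.2. The change is modest, and listing Part II already shows the last dose before onset.

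**Conclusion.** The point holds for AEs that start between consent and first dose and then increase in severity or become serious on drug. The SAP states a rule that misplaces them, and the protocol's treatment-emergent summaries have no definition to rest on.

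The conclusion assumes that worsening is entered as an update to the existing record and that assignment to screening means exclusion from the by-arm tables. Both are the natural reading; neither is stated outright. The effect is small: an upper bound of about 4 to 7% of AEs under a constant onset rate, of which an unknown part would worsen. The documents do not support a claim of a material bias in the safety comparison, of lost events, or of an error in counting AEs during follow-up. It is worth correcting because it concerns the secondary objective and is cheap to put right before database lock.

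**What to change.** In SAP 7.3.3.1:

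- Define a treatment-emergent AE as one that starts at or after the first intake, or that started earlier and increases in severity or becomes serious after it.
- Count these events under the randomised arm in all AE tables, and reserve the pre-treatment listing for the rest.
- State that for an aggravated pre-existing condition the AE onset is the date of aggravation.
- State whether worsening of an open AE is an update or a new record, so that the flag can be derived in the same way at all of the approximately 40 centres.

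Separately, reconcile Protocol 9.3.4 with the synopsis, 8.2 and 9.2 on when AE collection ends, and carry the result into the SAP.

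The cost is SAP wording and one derived flag. Protocol 9.3.4 already requires changes in severity and seriousness to be documented, so no new assessments are needed. If the CRF does not date those changes, a data query would be required for the few records concerned.
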